4. GENERAL DEFINITIONS AND NAMING CONVENTIONS

In order to avoid ambiguity during the analysis, a number of definitions and conventions for data handling are described here.

4.1 General Methodology and Presentation of the Results

The default summary statistics for quantitative (continuous) variables will be

- the number of subjects with data available (n),
- mean,
- standard deviation (SD),
- median,
- minimum (Min) and maximum (Max),
- 1st and 3rd quartiles (Q1 and Q3) for continuous demographic and laboratory data.

Mean and median will be presented to one more decimal place than the raw value. SD will be reported to two decimal places greater than the original value. The minimum, maximum, 1st and 3rd quartiles and 95% CI values will be presented with the same decimal precision as the raw value.

For qualitative (categorical) variables, the frequency count (n) and percentage (%) of subjects with non-missing data per category will be presented. “Missing” classification without percentage will be presented only if missing data will be in respective category.

Percentage values will be presented to one decimal place.

The denominator used for calculation of the percentages will be specified in a footnote to the tables for clarification.

4.2 Statistical Output Layout

All titles and column headers (consisting of one or several words) will be capitalized; articles, prepositions, and conjunctions, and “To” in infinitives will not be capitalized, except they are at the beginning of titles or headers.

All pages will be numbered according to the table/listing/figure to which the page belongs to. Every table/listing/figure will be numbered from page 1, “Page X of Y” at the bottom of each page.

The definition of baseline and endpoint value will be described in a footnote in every TLF where applicable. Other important definitions will also be presented if necessary.

Dates will be listed in the format: <yyyy>-<mm>-<dd> (e.g. 2003-11-20). Times will be listed in the format: <hh>:<mm> (e.g. 09:15) or in the format <hh>:<mm>:<ss> if seconds are collected. When date and time are collected, these are listed in the format: <yyyy>-<mm>-<dd>T<hh>:<mm> (e.g. 2003-11-20T09:15), <yyyy>-<mm>-<dd>T<hh>, or <yyyy>-<mm>-<dd>T<hh>:<mm>:<ss>.

Partial missing dates will be listed in the format <yyyy>-<mm> (e.g. 2013-11) if only day is missing or in the format <yyyy> (e.g. 2013) if month and day are missing.

Missing data including missing dates or times will be displayed in listings as blank fields, unless otherwise specified.

Listings will be sorted by subject’s number and visit number where applicable, unless specified otherwise.

4.3 Treatment Group Names and Labels

Since there is only one treatment group in this trial, statistical output will be presented only for the overall group. The labels to be used in the tables, listings and figures are defined in the table below.

Treatment Group Description	Treatment Group Label, which will appear in the TLFs
DRSP 4.0 mg	DRSP 4.0 mg

4.4 Visit Names and Labels

The names to be used in the analysis datasets and the labels to be used in the tables, listings and figures for the different trial visits are defined below.

Visit number	Visit name	Visit label, which will appear in the TLFs
10	Visit 1a (V1a, Screening Visit)	Visit 1a or V1a
11	Visit 1b (V1b, Medication Dispensation Visit, as soon as the results of the routine laboratory tests from V1a are available)	Visit 1b or V1b
20	Visit 2 (V2, Day 20 ± 2 of Medication Cycle 1)	Visit 2 or V2
30	Visit 3 (V3, Day 20 ± 2 of Medication Cycle 3)	Visit 3 or V3
40	Visit 4 (V4, Day 20 ± 2 of Medication Cycle 6)	Visit 4 or V4
50	Visit 5 (V5, Day 20 ± 2 of Medication Cycle 9)	Visit 5 or V5
60	Visit 6 (V6, Day $29 + 2$ of Medication Cycle 13) or EDV	Visit 6/EDV or V6/EDV
70	Visit 7 (V7, Follow-Up Visit, 10 to 14 days after V6)	Visit 7 (Follow-Up) or V7 (FU)

4.5 Days Numbering

All assessment dates will be related to the first day of IMP intake. This first day of IMP intake is referred to as Day 1. Day -1 is the day that is preceding Day 1 and Day 0 will not be defined. The assessment series is built up so that Day -2 is the day before Day -1 in the pre-treatment period, and Day 2 the second day on trial medication, etc.

4.6 Trial Periods

Date of the first IMP intake

The date of the first IMP intake will be defined as the date of the first IMP intake recorded in the treatment diary.

If such date is not available and subject did not return all IMP pills, Visit 1b date will be taken into account.

Date of the last IMP intake

The date of last IMP intake will be defined as the date of the last IMP intake provided in the eCRF “Trial Termination” section.

If such date is incomplete the following will be imputed:

- The date of the last day of the month, if month and year is available but the day is missing.

If such date is not available or only year is provided, last date of IMP administration recorded in subject's diary will be taken into account. If last date of IMP administration recorded in subject's diary is not available and subject did not return all IMP pills, the subject's last visit date will be taken into account.

Treatment period

The treatment period is defined as the period from the first IMP intake up to the last IMP intake.

Baseline value

Baseline value for a variable will be defined as Visit 1a value.

Absolute change

Absolute change from Visit 1a to each visit will be calculated as

$$\text{Absolute change from Baseline at Visit } <X> = \text{Value at Visit } <X> - \text{Baseline Value.}$$

Treatment cycle

Treatment cycles will be defined as 28 days periods starting on the day of the first IMP intake from the blister containing 28 tablets. No more than 13 completed cycles will be used for analysis.

Reference period

The treatment period will be grouped into reference periods as:

- Cycles 2-4
- Cycles 5-7
- Cycles 8-10
- Cycles 11-13

Overall period

- Cycles 2-13

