17 Serum potassium will only be evaluated for subjects that take medications that may increase serum potassium (ACE inhibitors, angiotensin – II receptor antagonists, potassium-sparing diuretics, potassium supplementation, heparin and aldosterone antagonists).

18 Drug accountability will only be performed in case a subject is discontinued prematurely or the IMP was collected from the subject. Otherwise the IMP will be counted by the investigator or designee at each visit and will be documented in the source documents only.

19 Pap smear not performed in subjects < 21 years of age.

20 On anticipated start date of Cycle 1 +2 days, the subject will be called by the site staff to confirm start date of IMP and e-diary compliance.

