2.3 Overall Trial Design

This trial is a prospective, multicenter, open-label, non-controlled trial in female subjects, age 15 or above who present to the clinic seeking contraception, who are postmenarcheal and premenopausal. Breastfeeding women are allowed to participate in the trial.

At V1a (screening), informed consent/assent will be obtained and the screening procedures will be performed. At V1b, after the results of the laboratory tests have confirmed the subject's eligibility, the subject will be provided with the investigational medicinal product (IMP) and an electronic diary and the subject will be instructed in their use. On anticipated start date of Cycle 1+2 days, the trial staff will call the subject for the confirmation of IMP start date. Afterwards, the subjects will attend Visits 2 to 5 at Day 20±2 of the 1st, 3rd, 6th and 9th cycle and Visit 6 at Day 29±2 of the 13th cycle. The follow-up (Visit 7) will take place 10-14 days after Visit 6. Once a month, on Day 10 (+ 2 days) of each cycle, the subjects will be contacted by the site staff to collect information on any adverse events which might have occurred.

The trial will include women who have never used hormonal contraceptives before consent/assent (naïve users), women who have not used hormonal contraceptives in the past three months before consent/assent or who have used hormonal contraceptives in the past but have a contraceptive-free time of less than three months before consent/assent (previous users) as well as women directly switching from another hormonal method (switchers). Women who have used hormonal contraceptives in the past but have a contraceptive-free time of less than three months before consent/assent are allowed to be included into the trial if they had at least one complete menstrual cycle before enrollment.

For naïve users and previous users, the first IMP intake will be on the first day of the next menstrual bleeding after Visit V1b. (If the menstrual bleeding starts in the evening, and the subject prefers to take her pill in the morning, then she may begin the first IMP intake the next day [Day 2 of the menstrual bleeding]). For a switcher, the first IMP intake will be on the day following the last active pill of the previous hormonal contraceptive. The subject is free to choose an intake time in the morning or evening

that suits her requirements. Breastfeeding women can start the first IMP any day starting six weeks after delivery.

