Listing EX15	Subjects with Long-Term Treatment of Any Medication That Might Interfere with the Efficacy of Hormonal Contraceptives Prior to Visit 1b
Listing EX16	Subjects Who Received Human Chorionic Gonadotropin or Co-Medication Containing Human Chorionic Gonadotropin Within a Month Prior to V1b
Listing EX17	Subjects with Progestin-Releasing Intra-Uterine Device or Contraceptive Implant Received or in Place within the Last 2 Months Prior to Visit 1a
Listing EX18	Subjects with history of clinically significant psychiatric illness or suicide risk

Additional trial conduct criteria deviations will be classified as follows:

Number	Name
Listing DRM01	Subjects Who Became Pregnant During the Study
Listing DRM02	Cycles when Vomiting or Diarrhea is Documented
Listing DRM03	Cycles with Administration of Prohibited Concomitant Therapy
Listing DRM04	Subjects Who did not Meet Inclusion/Exclusion Criterions
Listing DRM05	Listing and Chart with Treatment Cycles
Listing DRM06	IMP Gaps of More Than 48 Hours
Listing DRM07	Adverse Events of Special Interest
Listing DRM08	Non-Complete or Non-Correct Treatment Diary Records
Listing DRM09	Specification of Subject Withdrawn During Treatment
Listing DRM10	Specification of Subject Withdrawn During Screening
Listing DRM11	Protocol Deviation from eCRF
Listing DRM12	Scenarios for first IMP intake preceding V1b
Listing DRM13	Subjects with Partial Date of Last IMP Intake in eCRF
Listing DRM14	Treatment Compliance According to Drug Accountability
Listing DRM15	Subjects for Whom IMP Was Dispensed but Have No eDiary Records
Listing DRM16	Subjects Who Have Cyst Larger Than 30 mm

All decisions made during DRM will be documented in the DRM report.

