5.5 Efficacy Analysis

Primary and secondary efficacy analysis will be based on calculations of the PI in several different cases for non-breastfeeding women. The general formula of PI is

$$PI(<\text{set of cycles}>) = \frac{\sum \text{on-drug pregnancy} \in \{<\text{set of cycles}>\}}{\#\{<\text{set of cycles}>\}} \times 1300.$$

A two-sided 95% CI for the PI will be calculated assuming that events of pregnancy have a Poisson distribution. The CI will be calculated using the following equations from Gerlinger et al. [4]:

$$CI_{lower}(PI(<\text{set of cycles}>)) = \frac{1300}{\#\{<\text{set of cycles}>\}} \times CI_{lower}(\#\{\text{pregnancy} \in \{<\text{set of cycles}>\}\}),$$

$$CI_{upper}(PI(< set of cycles >)) \\ = \frac{1300}{\#\{< set of cycles >\}} \times CI_{upper}(\#\{pregnancy \in \{< set of cycles >\}\}),$$

where

$$CI_{lower}(\#\{pregnancy \in \{< set of cycles >\}\}) \\ = 0.5\chi^2(0.025; 2 \times \#\{pregnancy \in \{< set of cycles >\}\}),$$

$$CI_{upper}(\#\{pregnancy \in \{< set of cycles >\}\}) \\ = 0.5\chi^2(0.025; 2 \times \#\{pregnancy \in \{< set of cycles >\}\} + 1),$$

where $\chi^2(\alpha; n) = \alpha$ -Quantile of χ^2 -distribution with parameter n .

The following information from Pregnancy Notification forms will be taken:

- Subject ID number
- Estimated date of conception
- Method(s) Used to Estimate Conception Date

Efficacy analysis definitions

Term	Definition
Confirmed pregnancy	Subject reported a positive urine home pregnancy test and the pregnancy was confirmed by qualitative urine pregnancy test (β -hCG) and quantitative serum pregnancy test (β -hCG).
Suspected, non-confirmed pregnancy	Subject reported a positive urine home pregnancy test but confirmatory qualitative urine pregnancy test (β -hCG) and/or quantitative serum pregnancy test (β -hCG) are missing.
Suspected, subject confirmed not pregnant	Subject reported a positive urine home pregnancy test but confirmatory qualitative urine pregnancy test (β -hCG) and/or quantitative serum pregnancy test (β -hCG) are negative.
On-drug pregnancy	An on-drug pregnancy includes all conceptions that occur from Day 1 (the initiation of study medication) through seven days after the final tablet (active or placebo) is taken.

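### A missing first-intake date is replaced by the V1b dispensing date, which is normally too early for naïve and previous users and passes over the start date the site confirms by telephone

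*SAP*

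**What the plan says.** SAP 4.6 (Trial Periods) defines the first intake as the first one in the treatment diary. Its fallback is: "If such date is not available and subject did not return all IMP pills, Visit 1b date will be taken into account". Table 1 and SAP 4.4 identify V1b as the medication dispensation visit.

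SAP 2.3, like the protocol synopsis, does not tie the start of treatment to V1b:

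- Naïve and previous users: "For naïve users and previous users, the first IMP intake will be on the first day of the next menstrual bleeding after Visit V1b", or the day after in one evening-onset case.
- Switchers: "For a switcher, the first IMP intake will be on the day following the last active pill of the previous hormonal contraceptive".
- Breastfeeding women: any day from six weeks after delivery.

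The schedule provides for a check of the real date. Footnote 20 to Table 1 says "On anticipated start date of Cycle 1 +2 days, the subject will be called by the site staff to confirm start date of IMP", and SAP 2.3 repeats the call. SAP 4.6 does not name it as a source.

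The first-intake date then feeds day numbering (4.5), the FAS and MFAS condition on pregnancy at first intake (3.1), prior versus concomitant medication (5.3), treatment duration and compliance (5.4), the life-table origin (5.5.2) and the TEAE window (5.6.1). It also opens the pregnancy window in 5.5: "An on-drug pregnancy includes all conceptions that occur from Day 1 (the initiation of study medication) through seven days after the final tablet".

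SAP 3.3 plans Listing DRM15, "Subjects for Whom IMP Was Dispensed but Have No eDiary Records", but gives no rule for how those women are classified.

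**The concern.** Tablets are handed out at V1b, but a naïve or previous user is told to wait for her next menses. For her the imputed Day 1 will normally precede any tablet. The days in between are then handled as treatment in every output that uses the date.

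Two consequences matter more than the rest. First, a conception after V1b but before any tablet is a pre-treatment pregnancy on the true dates, yet on the imputed dates it can look like a contraceptive failure in the primary Pearl Index. Second, the only test attached to the fallback is that some pills were not returned. A woman who took her pack home and never opened it meets that test, so an intake date can be created for someone who had no intake.

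**Working it through.** **Figures in the plan.** The documents give no figure for this imputation and no count of women affected. The one plan figure needed is the target of 5000 evaluable cycles. It agrees closely with the stated sample size if dropouts are taken to contribute no cycles: 920 × 13 × (1 − 0.248) × (1 − 0.45) = 4947.

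**Who is affected.** The rule applies only when the diary has no first-intake date. SAP 5.4.1 first fills a missing regular intake time from the separate first-intake field. What remains is essentially the women with no diary intake at all and some pills outstanding.

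**Size of the date error (g).** For naïve and previous users, assume a 28-day cycle with V1b falling uniformly within it. Then g runs from 0 to 28 days, with a mean of 14. This does not carry over to switchers or breastfeeding women.

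**Compliance.** SAP 5.4.2 divides tablets dispensed minus returned by overall treatment duration. Take a woman who took one tablet a day for d days and returned the rest. The numerator is d, and the duration becomes d + g:

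| Days of tablets (d) | g = 0 | g = 14 | g = 28 |
|---|---|---|---|
| 28 | 100% | 28/42 = 66.7% | 28/56 = 50.0% |
| 84 | 100% | 84/98 = 85.7% | 84/112 = 75.0% |
| 364 | 100% | 364/378 = 96.3% | 364/392 = 92.9% |

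The same g days are added to the treatment period, the TEAE window and the overall life-table time.

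**Pearl Index denominator.** SAP 5.5 requires at least one diary intake entry for an exposure cycle, and evaluable and perfect cycles are subsets of exposure cycles. A woman with no diary intake who does not become pregnant therefore adds 0 cycles.

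**Pearl Index numerator.** Take a woman who conceives after V1b and before any tablet:

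1. With Day 1 imputed as V1b, she was not yet pregnant at first intake, so she meets that FAS and MFAS condition.
2. If the eCRF and the diary give no last-intake date and pills are outstanding, SAP 4.6 sets last intake to her last visit. The on-drug window then runs from V1b to seven days after that visit. If V1b was her last visit, imputed treatment lasts one day and the window closes seven days after V1b.
3. If the conception falls in that window, it is on-drug, and the pregnancy makes its own cycle an exposure and evaluable cycle without a diary entry.

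Each such pregnancy adds about 1300/5000 = 0.26. The table takes an assumed base of 10 pregnancies in 5000 cycles and adds one cycle per extra pregnancy. Limits are exact Poisson, with upper limit 0.5 × χ²(0.975; 2x + 2). The SAP prints a different upper-limit expression, which is a separate matter.

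| Misdated pregnancies | Pearl Index | 95% CI |
|---|---|---|
| 0 | 2.60 | 1.25 to 4.78 |
| 1 | 2.86 | 1.43 to 5.12 |
| 2 | 3.12 | 1.61 to 5.45 |
| 3 | 3.38 | 1.80 to 5.78 |

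**Safety percentages, if never-starters are included.** With m never-treated women in an assumed set of 995, a true 10% AE rate shows as 10% × (995 − m)/995. That is 9.95% for m = 5, 9.90% for m = 10 and 9.50% for m = 50.

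**The case against.** The other side has several good points.

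- **Set membership.** A reader might infer that never-starters enter the Safety Set, FAS and MFAS. No such rule is written. SAP 4.6 defines a date, while SAP 3.1 still requires that a dose was taken. Sets are assigned at the data review with drug-accountability and no-diary listings to hand (DRM14, DRM15), and SAP 5.1.1 recognises women who drop out before any intake. Their inclusion is a likely reading, because unreturned pills are treated as a sign of intake, but it is no more than that.
- **Pregnancies are reviewed.** SAP 3.3 has the data review, with a physician on the team, assign each pregnancy to a category and cycle. A naïve or previous user who conceives before her next menses would ordinarily not reach her start day, so the realistic case is a pregnant non-starter. It must also be a confirmed pregnancy to enter the primary table.
- **Direction.** Any Pearl Index error runs against the product.
- **V1b is not early for everyone.** Switchers and breastfeeding women follow other start rules, and Listing DRM12 anticipates intake before V1b.
- **Safety capture.** Dating from dispensing and keeping women with unreturned tablets favours AE capture. Classing them all as untreated could remove exposed women from the Safety Set.
- **Availability of the call date.** The documents require the call but do not say that its date is entered in the eCRF.

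All of this stands and limits the point. It does not explain why a date that contradicts the start rule for naïve and previous users should come ahead of one that the site is required to confirm. Correction at the data review is possible, but no written criterion governs it.

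**Conclusion.** The point holds as a date-handling defect confined to women with no diary intake date and outstanding pills. For naïve and previous users in that group, the imputed Day 1 is normally early, by 0 to 28 days under the 28-day-cycle assumption. The effect on an individual woman's duration and compliance can be large over short treatment and fades over a full year.

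The primary Pearl Index is exposed only through its numerator. A conception before the true start, or in a non-starter, could be counted if it falls in the imputed window and the data review does not remove it. The 0.26 is the effect of any single pregnancy at 5000 cycles; it is not evidence that one would be misassigned.

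A reader might go further and infer that untreated time inflates the Pearl Index denominator and so flatters the product. The diary-entry requirement for exposure cycles rules that out.

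The number of women affected is unknown and probably small. The change is worth making because it is specific and cheap.

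**What to change.** Amend SAP 4.6 so that, when the diary date is missing:

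1. The first-intake date is the start date confirmed at the Cycle 1 call or in another source record. For switchers, the stop date of the previous contraceptive recorded under SAP 5.3 can serve. That field is not defined as the last active pill, so the derived date is approximate.
2. V1b is used only as a last resort, and the woman is flagged as having unconfirmed intake.
3. No pregnancy is classed as on-drug solely because of an imputed V1b date.

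State in SAP 3.1 how the DRM15 women are assigned. Keep women with unconfirmed intake in the Safety Set by default, so that possibly exposed women and their AEs are not lost, and show Safety Set and MFAS results with and without them.

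The cost is a paragraph in 4.6, a sentence in 3.1, source retrieval for the DRM15 women and one sensitivity display. Where the call left no recorded date, the V1b fallback and its error remain, but they are visible.

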2.2 Trial Endpoints

2.2.1 Primary Efficacy Endpoints

The primary efficacy endpoint will be the Pearl Index (PI) based on evaluable cycles in non-breastfeeding women aged ≤ 35 years (at the time of trial enrolment).

PI = number of pregnancies*1300/number of evaluable medication cycles

An evaluable cycle is a cycle with intercourse without back-up contraceptive at least once per month based on the electronic diary question 'Did you have sexual intercourse since the beginning of the cycle?' and will be included in the primary analysis. If the cycle is not evaluable but the subject became pregnant in this cycle, the cycle has to be included in the analysis.

Pregnancies following premature termination of IMP will be excluded from the calculations if the estimated date of conception occurs later than seven days after the last tablet intake (active or placebo).

Date of conception will be determined by using the following information:

1. Ultrasound (the date of conception must be based on the most accurate method i.e. the first trimester ultrasound. Subsequent ultrasounds will not be allowed to change dating based on this initial assessment).
2. Ultrasound (in case the first trimester ultrasound was not performed)
3. Quantitative β -hCG
4. Qualitative urine β -hCG determination
5. Estimation of gestational age based on pelvic and/or abdominal examination or pregnancy outcome
6. Investigator's estimation in the absence of the above criteria

Medication cycle will be defined as 28 days starting with the administration of the first tablet from the blister containing 28 tablets and ending with the last day of intake.

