5.2.2 Substance Use

Substance use for the subjects include:

- Smoking status at screening visit (Non-smoker, Current smoker, Ex-Smoker, Nicotine replacement therapy)
- Smoking start date
- Number of cigarettes per day
- Date of smoking cessation
- Alcohol status (Abstainer, Moderate drinker, Excessive drinker)

Smoking duration (years)

Smoking duration in years for current smokers will be calculated as the difference between the start date of smoking and the date of Visit 1a using the following SAS function:

INT(YRDIF(<smoking start date>,<Visit 1a date>,'ACT/ACT'))

Non-smoking duration (years)

Non-smoking duration in years for ex-smokers will be calculated as difference between smoking cessation date and the date of Visit 1a using the following SAS function:

INT(YRDIF(<date of smoking cessation>,<Visit 1a date>,'ACT/ACT'))

Imputation of missing/incomplete dates:

Incomplete dates will be imputed in the following way:

for incomplete/missing smoking start date:

- the first day of the month, if only day is missing
- 1st of January, if the year is available but the day and month are missing
- if date is completely missing smoking duration will be set to missing

for incomplete/missing smoking cessation date:

- the last day of the month if only the day is missing, unless the year and the month of smoking cessation and Visit 1a are the same then the day of Visit 1a will be imputed
- 31st of December if only the year is available unless Visit 1a was performed at the same year then the day of Visit 1a will be imputed
- for completely missing dates Visit 1a date will be imputed.

Pack years smoking history:

A pack year is a unit for measuring the amount a subject has smoked over a long period of time. It will be calculated as follows:

$$\text{Number of pack years} = \frac{\text{number of cigarettes per day}}{20 \text{ (1 pack has 20 cigarettes)}} \times \text{smoking duration (years)}$$

Tables

No.	Name	Analysis set	Comments
Table 15.1.11.1.1	Substance Use	Safety	Smoking duration, number of cigarettes per day, pack-years and non-smoking duration will be summarized as continuous data. Smoking status and alcohol status will be presented by means of default frequency tabulation. Percentage will be based on the number of subjects with non-missing data in the SS. Data of centers 104 and 120 will be excluded.

Listings

No.	Name	Analysis set	Comments

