- **Probable:** A clinical event, including laboratory test abnormality, with a reasonable time sequence to administration of the drug, unlikely to be attributed to concurrent disease or other drugs or chemicals, and which follows a clinically reasonable response on withdrawal (dechallenge). Rechallenge information is not required to fulfil this definition.
- **Definite:** A clinical event, including laboratory test abnormality, occurring in a plausible time relationship to drug administration, and which cannot be explained by concurrent disease or other drugs or chemicals. The response to withdrawal of the drug (dechallenge) should be clinically

plausible. The event must be definitive pharmacologically or phenomenologically, using a satisfactory rechallenge procedure if necessary.

Related AEs include the categories “possible”, “probable” and “definite”.

Unrelated AEs include the categories “unrelated” and “unlikely”.

The relationship of an AE to the IMP will be defined as “Unknown” if relationship grade assessment is missing.

Treatment Emergent Adverse Events

An AE that emerges during treatment having been absent prior to treatment or worsens relative to the pre-treatment state is defined as treatment emergent adverse event (TEAE). All AEs with onset or worsening after first intake of IMP until 10 days after last intake of IMP are defined as treatment emergent.

Where only partial dates are present, the month and/or year may be sufficient alone for assignment of treatment emergent AEs but in cases where this is not possible these AEs will be considered as treatment emergent.

Serious Adverse Events

An AE or suspected adverse reaction is considered “serious” if, in the view of either the investigator or sponsor, it results in any of the following outcomes:

- Death
- A life-threatening
- Inpatient hospitalization or prolongation of existing hospitalization
- A persistent or significant incapacity or substantial disruption of the ability to conduct normal life functions
- Congenital anomaly/birth defect

Adverse Events of Special Interest

Adverse events of special interest will be defined as hyperkalemia and venous thromboembolism events. Hyperkalemia will be identified as AEs with preferred terms “Hyperkalaemia” and “Blood potassium increased”. Venous thromboembolism will be identified as embolic and thrombotic venous events and assignments will be handled by Medical Monitors after database closure.

Adverse events leading to trial termination

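### A last-tablet date with only the day missing is set to month end without a cap, so it can fall up to 30 days late and after the woman has left the trial

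*SAP*

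**What the plan says.** SAP 4.6 gives the only derivation of the last-tablet date. It starts from the Trial Termination section of the case report form: "The date of last IMP intake will be defined as the date of the last IMP intake provided in the eCRF". For an incomplete date it imputes "The date of the last day of the month, if month and year is available but the day is missing", with no further condition. The diary comes in only when the form holds less than that: "If such date is not available or only year is provided, last date of IMP administration recorded in" the subject's diary is then used. The last visit date is the final fallback, if the diary also fails and tablets were not all returned.

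Several analyses use this date:
- An on-drug pregnancy (5.5) is a conception from Day 1 "through seven days after the final tablet (active or placebo) is taken". The exclusion rule for the primary endpoint in 2.2.1 uses the same seven days.
- Adverse events (5.6.1) with onset from the first intake "until 10 days after last intake of IMP are defined as treatment emergent".
- Treatment duration (5.4.1), the compliance denominator (5.4.2), concomitant-medication status (5.3) and life-table censoring of women who did not become pregnant (5.5.2).

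Dates that could serve as a cap are collected: trial termination and last contact in 5.1.1. Section 5.4.1 adds each diary intake with its time. A comparable month-end rule elsewhere does have a limit: in 5.2.2 a smoking cessation date goes to month end "unless the year and the month of smoking cessation and Visit 1a are the same then the day of Visit 1a will be imputed".

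**The concern.** The month-end rule can produce an impossible date: a last tablet taken after the woman has had her final visit. The order of the rule is also odd. A form date with only the year leads to a recorded diary date, while a form date with year and month leads to an invented day, even when the diary has an entry in that month.

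At stake is the boundary between on-drug and off-drug. A conception or adverse event well after stopping can be classed as on-drug, against the SAP's own 7-day and 10-day limits. The same date feeds exposure, compliance and the life table, where the error does not all run in one direction.

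**Working it through.** The plan states no figure for the size of this error, so there is none to reproduce.

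**Inputs.** Month-end imputation (SAP 4.6); 7-day window (2.2.1, 5.5); 10-day window (5.6.1); factor 1300 (2.2.1); target of 5000 evaluable cycles (2.6); planned trial dates October 2014 to July 2017 (protocol synopsis). Assumption: the true stop day is uniform over the month.

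**1. Excess days.** With L days in the month and true last tablet on day d, excess E = L − d. The maximum is L − 1 and the mean is (L − 1)/2.
- 31-day month: maximum 30, mean 15.0
- 30-day month: maximum 29, mean 14.5
- February: maximum 27 or 28, mean 13.5 or 14.0

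Over every calendar day from October 2014 to July 2017 the mean is 14.7 days. E exceeds 7 days for 74% of days and 10 days for 64%. As a hand check, the share above 7 days is (L − 8)/L, which is 23/31 = 74% or 22/30 = 73%.

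**2. Windows after the true last tablet.**
- On-drug conception: 7 + E, at most 7 + 30 = 37 days, mean 21.7.
- Treatment-emergent events: 10 + E, at most 10 + 30 = 40 days, mean 24.7.

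**3. Illustration (hypothetical).** The last diary tablet is 3 March, the early discontinuation visit is 5 March, and the form gives March 2016 without a day. The imputed last tablet is 31 March, 26 days after that visit. The on-drug window ends on 7 April; counted from the diary tablet it would end on 10 March. The adverse-event window ends on 10 April instead of 13 March.

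**4. Primary Pearl Index.** The index is pregnancies × 1300 / evaluable cycles. One pregnancy kept in error adds 1300/5000 = 0.26. The denominator does not use the last-tablet date: under 5.5 an exposure cycle needs a diary intake entry or a pregnancy, and evaluable cycles are a subset of these. Imputed days therefore add no cycles, apart from at most the one cycle that a counted pregnancy brings with it (1 in 5000). The index can only rise.

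**5. Duration and compliance.** Duration is last intake − first intake + 1, so it grows by E. Compliance is (dispensed − returned)/duration. A woman who took every tablet should show 100%. At E = 30 she shows:
- after 28 days: 28/58 = 48.3%
- after 84 days: 84/114 = 73.7%
- after 364 days: 364/394 = 92.4%

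**6. Life table.** Each Kaplan-Meier factor is 1 − (events/number at risk). Later censoring keeps women who have stopped in the number at risk, so a factor can only stay the same or move closer to 1, and the cumulative pregnancy rate falls. A pregnancy wrongly kept as on-drug pushes the other way. The net size cannot be given without the number of affected women.

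**The case against.** The strongest reply is that the rule is deliberately cautious. In a single-arm trial meant to show a low Pearl Index, a later last-tablet date can only keep pregnancies in the numerator and events in the adverse-event tables. The SAP leans the same way elsewhere: adverse events with undecidable partial dates count as treatment emergent (5.6.1), and undecidable medications count as concomitant (5.3). This stands for the primary index and the event counts. It does not cover the life table, where later censoring lowers the rate, nor duration and compliance.

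Second, cases can be caught by hand. Listing DRM13 collects partial last-intake dates, and the data review meeting in 3.3 assigns each pregnancy to a category and cycle and settles open SAP issues before the SAP is final. This stands as a safeguard, but no written rule lets the meeting depart from month end.

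Third, the practical effect on adverse events is smaller than the window suggests. Follow-up is planned 10 to 14 days after Visit 6. If that also applies after the 5 March visit in the illustration, planned collection ends on 15 to 19 March. The extra time with planned data is then 14 March to 15–19 March, about 2 to 6 days, not the 28 days from 13 March to 10 April. Later events enter only if reported outside the schedule.

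Fourth, a reader might infer that the diary holds the true date and should simply replace month end. The documents do not support that. The diary holds the last recorded intake. The SAP plans a table of missing intake entries (5.4.1) and a listing of women given tablets who have no diary records (DRM15). A woman who stops recording before she stops taking tablets would get too early a date, and a true on-drug pregnancy could be dropped. That error would be anti-conservative, so the diary belongs in the primary rule only as a lower limit.

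**Conclusion.** The gap is real and modest. As written, the imputed last tablet can be up to 30 days late and can fall after the woman has left the trial. The 30-day maximum is a matter of the calendar; the 14.7-day mean rests on uniform stop days.

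For the primary Pearl Index and adverse-event counts the direction is conservative. The 0.26 per pregnancy assumes exactly 5000 evaluable cycles. It also requires a partial date, a conception in the added days that becomes known, and no correction at data review. Duration is overstated, compliance understated, and the censoring effect lowers the life-table rate.

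Three stronger readings are not supported. One is that overstated exposure dilutes the Pearl Index: its cycles come from diary entries or pregnancy. Another is that partial dates cluster among early dropouts, which is plausible but documented nowhere. The third is that DRM13 shows many women are affected: it is a planned listing and gives no number.

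**What to change.** In SAP 4.6, replace the month-end rule. When only the day is missing, impute the earliest of month end, trial termination date and last contact date, provided the result lies within the recorded month and year and is not before the last e-diary intake. Where these conditions cannot all be met, list the woman for the data review meeting as a data query and document the decision. In the illustration, with termination on 5 March, the cap gives an on-drug window to 12 March and an adverse-event window to 15 March.

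As a sensitivity analysis, use the last e-diary intake that falls in the known month, and report every pregnancy whose on-drug status depends on the imputed day. Report the number of women with an imputed day as well.

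The cost is a few sentences in 4.6, a small change to the derivation program and one extra run of the affected outputs. No new data are needed.
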